Eligibility	
Inclusion Criteria:
 
 • Age ≥ 18 years • A diagnosis of head and/or neck lymphedema • Must be able and willing to participate in all aspects of the registry and provide informed consent prior to registry participation • Head and chest measurements within the following: 
 ○ Crown of head circumference: ≤ 72 cm ○ Chest circumference: ≤ 158 cm • Prescribed the Flexitouch system or Flexitouch Plus 
Exclusion Criteria:
 
 • Uncontrolled hyperthyroidism or parathyroidism (for which endocrinologist recommends against neck compression) • Carotid sinus hypersensitivity syndrome • Symptomatic carotid artery disease, as manifested by a recent transient ischemic attack (within 30 days), ischemic stroke, or amaurosis fugax (monocular visual ischemic symptoms or blindness) • Symptomatic bradycardia in the absence of a pacemaker • Internal jugular venous thrombosis (within 3 months) • Increased intracranial pressure or other contraindications to internal or external jugular venous compression • Acute radiation dermatitis, unhealed surgical scar, unhealed or open wound(s), or surgical flap less than 6-8 weeks post-operative

	
 • Facial or head and neck dermal metastasis • Acute facial infection (e.g., facial or parotid gland abscess) • Any condition in which increased venous and lymphatic return is undesirable • Heart failure (acute pulmonary edema, decompensated acute heart failure) • Subject is pregnant or trying to become pregnant • Acute venous disease (acute thrombophlebitis, acute deep venous thrombosis, acute pulmonary embolism)
Subject Participation Duration	Approximately 6 months
Sample Size	Open

TABLE OF CONTENTS

1.0	Contact Information	7
1.1	Sponsor Contact Information	7
2.0	Abbreviations	7
3.0	Introduction	8
3.1	Background and Rationale	8
3.2	Device Description	8
4.0	Registry Objective	9
5.0	Registry Design	9
5.1	Endpoints	9
5.2	Subject Selection	10
5.3	Registry Duration	11
6.0	Registry Visit Summaries	11
6.1	Screening/Baseline Visit #1	11
6.2	Device Training Visit #2 (Day 0)	11
6.3	Week 2 Phone Call Visit #3 (Day 14±3)	12
6.4	Month 1 Clinic Visit #4 (Day 28±5)	12
6.5	Month 2 Phone Call Visit #5 (Day 56±5)	12
6.6	Month 3 Clinic Visit #6 (Day 84±5)	12
6.7	Month 6 Clinic Visit #7 (Day 168±14)	13
6.8	Registry Exit	13
7.0	Registry Schedule of Activities	14
8.0	Registry Procedures	14

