5.0 Registry Design

This multi-center, prospective, observational, registry will follow patients with head and neck lymphedema who are using the Flexitouch system or Flexitouch Plus. Data collection will occur at Baseline and Days 14, 28, 56, 84, and 168.

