7.0 Registry Schedule of Activities

Procedures	Visit 1 (in clinic)	Visit 2 (in home or clinic)	Visit 3 (phone call)	Visit 4 (in clinic)	Visit 5 (phone call)	Visit 6 (in clinic)	Visit 7 (in clinic)
	Screen/ Baseline	Day 0	Week 2 (Day 14 ± 3 Days)	Month 1 (Day 28 ± 5 Days)	Month 2 (Day 56 ± 5 Days)	Month 3 (Day 84 ± 5 Days)	Month 6 (Day 168 ± 14 Days)
Informed Consent	X						
Device Training		X					
Pregnancy Test (if applicable)	X						
Medical History	X		X*	X*	X*	X*	X*
Vital Signs (if applicable)	X			X		X	X
Lymphedema Evaluation	X						X
Range of Motion (Neck, mouth, shoulders)	X			X		X	X
Assess Swelling	X			X		X	X
QOL (EORTC C30)	X			X		X	X
Symptoms (EORTC H+N35)	X			X		X	X
Assess Pain (VAS)	X			X		X	X
Ease of Use and Satisfaction Survey							X
Complications/ AEs/SAEs			X	X	X	X	X
Device Use Evaluation			X		X		
Compliance			X	X	X	X	X

* Change in medical history.

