15.0 Statistical Methods

For continuous variables, descriptive statistics will include the number of subjects (n), mean, standard deviation, median, inter-quartile range, minimum, and maximum, based upon subjects with reported data for the variable being analyzed.

Frequencies (numerator and denominator), percentages, and 95% confidence intervals will be displayed for categorical data. Percentages by categories will be based on the number of subjects with no missing (unreported) data for the specific variable being analyzed and the count of the patients for each individual level of the categorical variable (the level specific numerators). Percentages will add up to 100%, unless otherwise indicated.

There are no plans to impute missing data and there are no plans to explicitly report missing data (counts and/or percentages) in the tables for all variables as part of the planned study report content. Variations in the reported sample sizes within and/or between relevant tables can be used to ascertain insights into unreported data. In some cases, unreported data may be due to it not being clinically relevant to a particular patient or may represent expected data that was not collected. Selected analyses pertaining to unreported and/or missing data may be discussed and considered as future findings warrant.

The observational nature of the study suggests that the statistical focus will be on estimation and hypothesis generation and not hypothesis testing. Though p-values will be reported as apropos, point estimates, and 95% confidence intervals will be used to guide exploratory analyses for potentially clinically meaningful differences or changes to be discussed and evaluated.

Inter-group (e.g., bivariate) comparisons, when performed, will utilize chi-square, ANOVA, t-test, and appropriate non-parametric tests, unless otherwise specified.

Multivariable models (e.g., linear regression or logistic regression) may be used to assess the predictive relationships and control for possible confounding imbalances of selected multiple variables to specific outcome measures of interest.

Any formal null hypothesis-based statistical comparisons will be made using two sided tests at the $\alpha=0.05$ significance level unless specifically stated otherwise. All null hypotheses will be of no inter-group difference, all alternative hypotheses will be two-sided, unless specifically stated otherwise.

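### Section 15.0 makes unadjusted tests the default for comparing non-randomised groups and never names the baseline value as a covariate, so such comparisons may carry baseline differences into the estimate and its interval

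*Combined protocol and SAP*

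**What the plan says.** The Registry Design section (5.0) reads: "This multi-center, prospective, observational, registry will follow patients with head and neck lymphedema who are using the Flexitouch system or Flexitouch Plus". Nobody is randomised, and no comparison groups are defined anywhere.

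Three statements in 15.0 Statistical Methods bear on group comparisons:

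- The default tests: "Inter-group (e.g., bivariate) comparisons, when performed, will utilize chi-square, ANOVA, t-test, and appropriate non-parametric tests, unless otherwise specified".
- Multivariable linear or logistic models "may be used to assess the predictive relationships and control for possible confounding imbalances of selected multiple variables". The variables are not listed, the baseline value of the outcome is not mentioned, and no rule says when a model is used.
- The hypotheses: "All null hypotheses will be of no inter-group difference, all alternative hypotheses will be two-sided, unless specifically stated otherwise".

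The same section puts estimation ahead of testing. It says that point estimates and 95% CIs will guide the exploratory work, with p-values reported where apt.

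On the data, 6.1, 6.7 and the schedule in 7.0 show that range of motion, swelling, EORTC C30, EORTC H+N35 and the pain VAS are all recorded at Visit 1 and at Visit 7 (Day 168). The ease-of-use and satisfaction survey is given only at Visit 7. Section 5.1.2 defines quality of life, pain and swelling as changes; 5.1.1 speaks of improvement in symptoms and function.

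**The concern.** The unadjusted test is what *will* be used; the adjusted model is what *may* be used. Groups in this registry would arise from what was prescribed, how severe the disease is, or where the patient is treated. Such groups can differ at the start on the very measure being compared.

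An unadjusted comparison of Day 168 values then carries part of the starting gap forward. A comparison of change scores can make the group that started worse seem to gain more. In either case the point estimate is shifted and the interval moves with it, so the stated preference for estimates over tests gives no protection. Even with balanced baselines, leaving out a baseline value that is already collected gives wider intervals than necessary.

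What is at stake is any statement that one device model, stage or site did better than another. Because the stated null hypotheses are inter-group by default, formal p-values would fall on exactly these comparisons.

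**Working it through.** The plan states no sample size target, effect size, SD or baseline-to-follow-up correlation, so it has no figure of its own to reproduce. What follows is an illustration.

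**Assumed inputs (none from the documents):** equal SD of 1 within groups at baseline and Day 168; correlation ρ from 0.3 to 0.8; one group starting 0.3 SD higher; 50 subjects per group. **From 15.0:** two-sided α = 0.05.

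**Precision with balanced baselines.** The variance per subject is 1 for the Day 168 value, 2(1 − ρ) for change, and 1 − ρ² after baseline adjustment. The ratios are therefore 1 − ρ² against the Day 168 value and (1 − ρ²) / [2(1 − ρ)] = (1 + ρ)/2 against change.

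**Bias if there is no group effect given baseline**, so that both groups regress towards one common mean. The false difference is 0.3ρ on Day 168 values and −0.3(1 − ρ) on change. The baseline-adjusted difference is 0.

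| ρ | Adjusted / Day 168 variance | Adjusted / change variance | False difference, Day 168 (SD) | False difference, change (SD) |
|---|---|---|---|---|
| 0.3 | 0.91 | 0.65 | 0.09 | −0.21 |
| 0.5 | 0.75 | 0.75 | 0.15 | −0.15 |
| 0.7 | 0.51 | 0.85 | 0.21 | −0.09 |
| 0.8 | 0.36 | 0.90 | 0.24 | −0.06 |

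**Rejection rate of the nominal 5% test**, normal approximation, standard error √(2 × variance / 50). For ρ = 0.5 on Day 168 values the standard error is √(2/50) = 0.20, the shift is 0.15/0.20 = 0.75 standard errors, and the rejection rate is about 12%. At ρ = 0.3, 0.5 and 0.7 the rates are 7%, 12% and 18% on Day 168 values, and 14%, 12% and 9% on change.

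**The opposite assumption.** Suppose instead that the groups have different stable means and neither truly changes, as could happen with groups defined by stage. The change-score difference is then 0, the Day 168 difference is the full 0.3 SD, and the baseline-adjusted difference is 0.3 − 0.3ρ = 0.3(1 − ρ), which is 0.21 SD at ρ = 0.3 and 0.06 SD at ρ = 0.8. This error is as large as the change-score error in the table, but it now falls on the adjusted model.

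**Precision when the baselines differ.** With equal groups and a gap of d SD, the adjusted variance is multiplied by 1 + d²/4. For d = 0.3 this is 1.0225, which is negligible. For large gaps it is not. At ρ = 0.8, adjustment loses its advantage over change when 0.90 × (1 + d²/4) = 1, that is at d of about 0.67. At d = 1 the ratio is 0.90 × 1.25 = 1.125.

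**The case against.** Five points can be made in the plan's favour.

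1. *The section already allows for confounding.* The sentence after the list of tests provides models for this purpose. That is true, and it reduces the gap to one of commitment: the model is optional, the baseline value is not named, and the analyst may choose after seeing the data.

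2. *The baseline is not ignored.* A reader might infer from the list of tests that each subject's starting value is discarded. The documents do not support that. A t-test or ANOVA can be run on change, and three secondary endpoints are defined as changes. What can be said is that the named tests do not adjust for baseline, and that 15.0 does not say whether they would be applied to change or to Day 168 values.

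3. *No such comparison is planned.* Group comparisons are conditional and exploratory, and device model, stage or site are only plausible examples. This stands and limits the weight of the point. It does not remove it, because the default would govern any comparison that is made.

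4. *Adjustment is not free and not always right.* This also stands. Change-score and baseline-adjusted results can disagree for pre-existing groups, nothing in the documents settles which assumption holds, and a large baseline gap costs precision.

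5. *The listed tests are still needed.* They are. Stage and the presence or absence of clinical findings at Visit 7 (8.2), device-related adverse events and the satisfaction survey would otherwise have no inter-group method.

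**Conclusion.** The point holds in a limited form. Section 15.0 makes the weaker method the default for continuous outcomes in non-randomised groups, although the data for a better one are collected as routine. Estimates and intervals from such comparisons may therefore contain baseline differences.

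The size cannot be fixed from the documents. The illustrative false differences (0.06 to 0.24 SD in magnitude for a 0.3 SD gap) and the rejection rates of 7% to 18% rest on the assumed gap, correlation and group size, on equal SDs, and on both groups regressing to a common mean. The variance savings (9% to 64% against Day 168 values, 10% to 35% against change) apply when baselines are balanced.

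A reader might go further and infer that the registry's primary results are biased, or that a device-model difference will be reported falsely. Neither follows. The objective and endpoints concern outcomes over 168 days in subjects who all use the device, and these within-subject results do not depend on the inter-group tests. Nor would adjustment make the groups comparable in other respects; residual confounding remains. This is a worthwhile, inexpensive improvement to an exploratory part of the plan.

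**What to change.** Add to 15.0:

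- Any inter-group comparison of a continuous Day 168 outcome with a baseline measurement (H+N35, range of motion, C30, VAS, swelling) names the groups compared. Its main estimate is the group difference with 95% CI from a linear model with the baseline value of the same measure as covariate.
- Baseline lymphedema stage is added where numbers allow and where stage is not the grouping factor. The condition on numbers matters because stage has five categories and the sample size is open.
- The unadjusted difference in change is reported beside it as supportive, with a note that the two can disagree when groups are formed by disease severity.
- Chi-square, t-test, ANOVA and non-parametric tests remain for categorical outcomes, adverse events, the satisfaction survey and the description of baseline characteristics.

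The cost is a few sentences and slightly more analysis in R, which the plan already names; no new data are needed. The downsides are some loss of precision if the baseline gap is large, and residual confounding, which the report should acknowledge.

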5.1 Endpoints

5.1.1 Primary Endpoints

To evaluate symptom and function improvement after 168 days (approximately 6 months) of treatment with the Flexitouch system or Flexitouch Plus based upon:

- Symptom survey (EORTC H+N35); and
- Range of motion measures (neck, mouth, and shoulder).

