6.7 Month 6 Clinic Visit #7 (Day 168±14)

Approximately 168 days after the subject begins using the prescribed treatment, or upon early termination of a subject (if possible), he or she will return to the clinic and undergo the following procedures at Visit 7:

- Changes to medical history;
- Obtain vital signs (if collected as part of standard of care);
- Complete lymphedema evaluation;
- Obtain ROM measurement (Appendix B);
- Obtain swelling measurements (Appendix C);
- Have subject complete the EORTC C30 (Appendix D), EORTC H+N35 (Appendix E), VAS (Appendix F), and Ease of Use and Treatment Satisfaction Survey (Appendix G);
- Record device-related adverse events (NOTE: Compare events to pre-existing conditions documented in Medical History to determine if the event is a new event, a worsening of a pre-existing event, or just a reoccurrence of a pre-existing event); and
- Review treatment compliance with subject.

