9.0 Subject Withdrawal or Early Termination

Subject participation may be terminated prior to completing the registry for any of the following reasons:

- **Withdrawal of Consent**
Subjects may withdraw their consent to participate at any time. If a subject withdraws consent, previous information that has already been obtained will be available for analysis.
- **Lost to Follow-up**
A certified, return-receipt letter must be sent to the subject after 2 attempts to reach the subject by telephone have failed. The subject will be considered lost to follow-up if this communication is unsuccessful.
- **Adverse Event**
Subject experiences an adverse event that in the investigator's clinical judgement necessitates discontinuation of their participation in this registry.
- **Discretion of the Principal Investigator**
Subjects may be withdrawn at the investigator's discretion in the event of subject noncompliance, changes in the subject's health, or other reasons based on the investigator's clinical judgment.

When a subject withdraws prior to completing the registry, all effort should be made to complete Visit 7 prior to documenting the reason for withdrawal in the subject's medical record.

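### Does Section 15.0 leave the primary 168-day change undefined by stating its null and tests only for comparisons between groups?

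*Combined protocol and SAP*

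**What the plan says.** Section 5.1.1 gives the primary aim as "To evaluate symptom and function improvement after 168 days (approximately 6 months) of treatment", judged by the EORTC H+N35 and by neck, mouth and shoulder range of motion. Sections 6.1 and 7.0 have both measured at Baseline, and Section 7.0 repeats them on the same subjects at Visits 4, 6 and 7.

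Section 6.7 places Visit 7 at Day 168±14 and describes its timing as "Approximately 168 days after the subject begins using the prescribed treatment, or upon early termination of a subject (if possible". For withdrawals, Section 9.0 adds that "all effort should be made to complete Visit 7 prior to documenting the reason for withdrawal".

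Section 15.0 summarises continuous variables "based upon subjects with reported data for the variable being analyzed", with no imputation. It says that "the statistical focus will be on estimation and hypothesis generation and not hypothesis testing", and that point estimates and 95% confidence intervals "will be used to guide exploratory analyses for potentially clinically meaningful differences or changes to be discussed and evaluated". On testing it says "Inter-group (e.g., bivariate) comparisons, when performed, will utilize chi-square, ANOVA, t-test, and appropriate non-parametric tests, unless otherwise specified", and then "All null hypotheses will be of no inter-group difference, all alternative hypotheses will be two-sided, unless specifically stated otherwise".

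**The concern.** Sections 5.0 and 5.1 describe device users followed over time, with no control group, so the primary question concerns change within subjects. Yet the only null in Section 15.0 is one of no difference between groups. Its named tests are tied to such comparisons, and the room it leaves for exceptions is never used. Section 15.0 mentions neither primary instrument, Baseline, Day 168 nor pairing. If a p-value were reported for a primary measure, the stated null would not fit it.

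A second question remains even if everyone uses a paired change. Values collected at early exit carry the Visit 7 label by design. One analyst could take every reported Visit 7 value, while another could keep only those inside the visit window. The two would then average over different subjects. Section 9.0 lists adverse events, noncompliance and changes in health among the reasons for leaving, so early exits may differ from completers. At stake is whether the main estimate of the registry is uniquely defined.

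**Working it through.** The documents give no target sample size, power, SD, effect size, correlation or dropout rate, so there is no planned figure to reproduce. The check is mainly a reading of the sections together. The arithmetic below gives scale only, on assumed inputs.

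**1. Is the contrast recoverable?** Section 5.1.1 fixes the measures and the time point. Improvement has no meaning without a starting value, and Section 6.1 collects one for each measure. Section 7.0 shows the same subjects measured again at Visit 7. The contrast is Day 168 minus Baseline in subjects with both values. Section 15.0 supplies n, the point estimate and the 95% confidence interval, and it refers to changes as well as differences.

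**2. Does the inter-group sentence prescribe a wrong test?** It follows a sentence limited to formal null-hypothesis comparisons, and the named tests apply only when inter-group comparisons are made. Such comparisons have a natural use here, since the registry covers two devices and may examine subgroups. Nothing tells the analyst to treat Baseline and Day 168 as independent groups.

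Suppose someone did so anyway, with equal SDs at the two visits and complete pairs. The point estimate would be the same. The ratio of standard errors would be √(2/n) ÷ √(2(1−ρ)/n) = 1/√(1−ρ). For assumed correlations ρ = 0.3, 0.5 and 0.7 this is 1.20, 1.41 and 1.83. The intervals would be too wide, which does not favour the device.

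**3. Which Visit 7 values count?** The window runs from 168 − 14 = Day 154 to 168 + 14 = Day 182.

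- For leaving out earlier values: the endpoint in Section 5.1.1 is the state after 168 days of treatment, and a subject who left on, say, Day 40 has no such value.
- For including them: the Visit 7 label, together with the rule of using subjects with reported data. That rule refers to the variable being analysed and does not define the variable by visit label.

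The first reading follows from the endpoint and the schedule. The second needs an added assumption. Day 0 fixes the follow-up schedule (Section 6.2) and the exit date and reason are recorded (Section 6.8), so early values can be identified.

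**4. How far apart could the two estimates be?** Let e be the share of Baseline/Visit 7 pairs that come from early exits, and g the gap in mean change between early exits and completers. The estimates differ by e × g. With assumed e of 5–20% and g of 0.3–0.5 SD:

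- lowest: 0.05 × 0.3 = 0.015 SD
- highest: 0.20 × 0.5 = 0.10 SD

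The sign depends on whether early exits did worse or better.

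Alternatively, assume that gain is linear in time and exits are uniform over Days 0–153. The mean exit day is 153/2 = 76.5. Including early values then lowers the estimate by e × (1 − 76.5/168) = e × 0.545, that is 2.7%, 5.4% and 10.9% for e = 5%, 10% and 20%.

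**The case for a change.** The strongest case for a change is that estimation needs a defined quantity at least as much as testing does. The ±14 days is written as a visit window and nowhere as an analysis window. An early Visit 7 value counts as reported, so the n in a table would not reveal it, and Section 15.0 does not plan to tabulate missing data. Section 5.3 foresees analyses at various times, so successive reports could handle early values differently. Section 15.0 also allows p-values where suitable. A few sentences would settle all of this without new data.

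Part of this stands: no sentence in the documents states the rule for early-termination values, and writing one down would do no harm. The rest carries less weight. A p-value on a primary measure is optional under a plan that disclaims testing, and an analyst who reports one would test zero within-subject change. The two readings of Visit 7 are not equally supported. The possible difference rests wholly on assumed rates and gaps, because the documents supply none, so it does not show that the results of this registry would be materially affected. Consistency across reports is a matter of ordinary analytic practice, and the exit data allow early values to be shown separately at any time.

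**Conclusion.** No change to the plan is needed. It is true that Section 15.0 words its null and tests for group comparisons, and that the status of Visit 7 values taken before Day 154 is unstated. Neither point prescribes an incorrect analysis or makes a stated figure wrong. In an exploratory, estimation-led registry of open size, the sections read together lead to a paired Baseline-to-Day-168 change with n and a 95% confidence interval. Values from early exits then fall naturally outside the 168-day endpoint.

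The remaining latitude is 0.015–0.10 SD in either direction if 5–20% of pairs come from early exits whose mean change differs by 0.3–0.5 SD. It is 2.7–10.9% of the estimate under linear gain and uniform exits over Days 0–153. All of these inputs are assumptions. The conclusion rests on the reading of Sections 5.1.1, 6.1, 6.7, 7.0 and 15.0 together, and on the plan's stated priority of estimation over testing.
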